12-lead electrocardiogram	X		X	X	X	X	X	X	X	X	X	X	X		X					X	Sec. 8.3.3. Predose and 3.5 hrs postdose on each dosing days	
Laboratory Procedures/Assessments																						
Safety Lab	Hematology and Chemistry	X	X	X		X		X	X	X	X	X	X		X		X	X	X	X	Sec. 8.4.3, 10.2 (Appendix 2) and 10.9 (Appendix 9).	
	aPTT/PT at Local Lab	X		X(3)		X(2)	X(2)	X(2)	X	X(2)	X	X(2)	X	X	X	X	X	X	X	X	Day 1: Predose, 1 and 12 hrs postdose. Predose may be performed within 3 days of dosing. Days 3, 5, 8, 15 and 22: 1 and 12 hrs postdose.	
	Hemoccult Test		X		X		X	X	X	X	X	X	X		X	X	X	X	X	X	Sec. 8.4.3, 8.11.6, 10.2 (Appendix 2) and 10.9 (Appendix 9).	
	HIV/hepatitis Screen	X																			Per site SOP	
	Serum/saliva Drug and Alcohol Breath Test	X	X	X																	Per site SOP	
	Serum Follicle Stimulating Hormone (FSH)	X																			Postmeno-pausal/oophorectomized female participants only	
	Serum β-Human Chorionic Gonadotropin (β-hCG)	X																		X	Female participants only	
	AE/SAE review	X																		X	Sec. 8.5 and 10.3 (Appendix 3)	

Study Period	Screening ≤28 days to Day 1	Intervention																		Post- study	Notes		
		Week 1		Week 2		Week 3		Week 4		Post Week 4													
Scheduled Week/Day	Scn1	Scn2 ^d	1	2	3	5	8	10	15	17	22	23	24	26	29	35	42	49	63	81	111	Sec. 8.11 for Visit Requirements and Sec. 8.11.6 for Timing of Procedure	
			NA	NA	NA	NA	NA	±1	NA	±1	NA	NA	NA	+1	NA	±2	±2	±2	±3	±3			
Pharmacokinetics																							
Blood for Plasma MK-2060 Assay			X(3)	X	X(2)	X(2)	X(2)	X	X(2)	X	X(3)	X	X	X	X	X	X	X	X	X	Sec. 8.7 Days 1 & 22: predose, 1h (within 5 min end of infusion), 12h. Days 3, 5, 8 & 15: predose, 1h (end of infusion). See footnote e, f.		
Pharmacodynamics																							
Blood for PT/aPTT/ FXI Activity by Central Lab			X(2)	X	X	X	X	X	X	X(2)	X	X	X	X	X	X	X	X	X	X	Sec. 8.8, Days 1 and 22 (2 draws): predose and 1h (within 5 min end of infusion).		
Blood for Fibrin Generation Assay			X(2)	X	X	X	X	X	X	X(2)	X	X	X	X	X	X	X	X	X	X			
Blood for biomarker(s) of inflammation (e.g., hsCRP) Assay			X				X		X		X				X	X	X	X	X	X			
Biomarkers																							
Blood for plasma anti-drug antibody			X							X		X						X	X	X	X	See Section 8.9 On dosing Days 1, 15, and 22: draw sample at predose.	
Blood for Genetic Analysis			X																			See footnote c.	
5-D Pruritus Scale												X				X							

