a.	Blood samples at each dosing day (i.e. Days 1, 3, 5, 8, 15 and 22 postdose will be collected in the opposite arm from the dialysis vascular access site.																						
b.	On site Hemodialysis: Pre-dose blood sample collections will be collected prior to HD initiation and 4hr samples collected immediately after the conclusion of HD.																						
c.	Blood for Genetic Analysis: This sample should be drawn for planned analysis of the association between genetic variants in DNA and drug response. This sample will not be collected at that site if there is either a local law or regulation prohibiting collection, or if the IRB/IEC does not approve the collection of the sample for these purposes. If the sample is collected, leftover extracted DNA will be stored for future biomedical research if the participant (or their legally acceptable representative) provides documented informed consent for future biomedical research. If the planned genetic analyses are not approved, but future biomedical research is approved and consent is given, this sample will be collected for the purpose of future biomedical research. Blood for genetic analysis should be collected only once per participant after randomization. If a participant re-enrolled into Part 2, a blood for genetic analysis sample is not needed if collected in Part 1.																						
d.	Screening 2 may be performed within 80 hours prior to Day 1.																						
e.	Leftover main study plasma will be stored for future biomedical research if the participant (or their legally acceptable representative) provides documented informed consent for FBR.																						
f.	All pre-dose PK should be taken prior to initiation of dialysis on that day.																						

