8.9.1 Blood Collection for PT, aPTT, FXI Activity and FGA Assay

Part 1: PT and aPTT at screening, 1 hour, 12 hour, 48 hours, Day 5, Day 8, Day 12, Day 15, Day 22, and Day 90 post-dose will be performed locally for safety monitoring. All other pre-dose and post-dose PT and aPTT, as well as FXI activity will be performed at a central vendor for PK/PD analysis. FGA assays will be performed by the Sponsor. Sample collection, storage, and shipment instructions for the PT, aPTT, FXI activity, and FGA assays will be provided in a separate trial Study Operations Manual by the Sponsor. The primary data for statistical analysis and modeling will be based on the information from the central vendor.

Part 2: PT and aPTT at screening, predose, 1 hour, 12 hour postdose on each dosing day (Days 1, 3, 5, 8, 15 and 22), Day 10, Day 17, Day 23, Day 24, Day 26, Day 29, Day 35, Day 42, and Day 111 post-dose will be performed locally for safety monitoring. All other pre-dose and post-dose PT and aPTT, as well as FXI activity will be performed at a central vendor for PK/PD analysis. FGA assays will be performed by the Sponsor. Sample collection, storage, and shipment instructions for the PT, aPTT, FXI activity, and FGA assays will be provided in a separate trial Study Operations Manual by the Sponsor. The primary data for statistical analysis and modeling will be based on the information from the central vendor.

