The posterior probability that the true fold-increase from baseline in aPTT is at least 1.5 will be calculated at each of the three weekly time points assuming normality and using a non-informative prior. A 60% posterior probability for at least one of the three time points that also exhibits an acceptable safety profile will satisfy the secondary pharmacodynamics hypothesis. In addition, the proportion of subjects with at least 1.5 fold increase in aPTT 168 hours after the last dose will be tabulated.

FXI activity levels, FGA and PT will be evaluated in a similar fashion. Additional model-based analysis may be employed to further explore PD endpoints over time.

Descriptive statistics will be provided for PD endpoints by treatment and time.

PK-PD

The relationship between plasma concentrations and aPTT, FXI activity, FGA, and PT will be explored graphically. Upon visual inspection, additional model-based analysis may be employed to further explore the PK/PD relationship.

General

For all analyses, data will be examined for departures from the assumptions of the statistical model(s) as appropriate; e.g., heteroscedasticity, nonnormality of the error terms.

Distribution-free methods may be used if a serious departure from the assumptions of the models(s) is observed, or suitable data transformations may be applied.

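### Does the untimed central-lab aPTT draw on some Part 2 dosing days undermine the 1.5-fold rule?

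*Combined protocol and SAP*

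**What the plan says.** Section 9.6 (Part 2) models log fold change in aPTT at three weekly times. The probability that the true fold rise "is at least 1.5 will be calculated at each of the three weekly time points assuming normality"; 60% at any one of them, with acceptable safety, is enough. The hypothesis in sections 3 and 9.3 concerns one time, 168 hours after the last dose. Section 8.9.1 makes central-vendor results the primary data.

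For Part 2 draw times, the Schedule of Activities (1.3.2) reads:

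- Central PT/aPTT/FXI row: "Days 1 and 22 (2 draws): predose and 1h (within 5 min end of infusion". No time is given for other dosing days.
- Plasma MK-2060 row: "Days 3, 5, 8 & 15: predose, 1h (end of infusion".
- Local aPTT/PT row: "Days 3, 5, 8, 15 and 22: 1 and 12 hrs postdose", plus a predose sample on Day 1.
- Anti-drug antibody row: "On dosing Days 1, 15, and 22: draw sample at predose".
- Footnote f: "All pre-dose PK should be taken prior to initiation of dialysis on that day". Footnote b puts pre-dose blood in general before dialysis starts.

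Section 8.9.1 lists for the local laboratory "PT and aPTT at screening, predose, 1 hour, 12 hour postdose on each dosing day (Days 1, 3, 5, 8, 15 and 22", with further named days, and then says "All other pre-dose and post-dose PT and aPTT, as well as FXI activity will be performed at a central vendor for PK/PD analysis".

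**The concern.** The row that supplies the primary data is the one that leaves dosing-day draws untimed, although section 4.1 makes the Schedule the place for prescribed times. Infusion starts 30 minutes into dialysis (8.1.8.1), so a 1-hour draw falls at peak concentration and during dialysis, where 6.6.1 expects heparin to lengthen the local-laboratory aPTT. If such a draw counted as a weekly value, one peak reading could satisfy a claim about 168 hours. Section 8.9.1 seems to add to the difficulty: taken literally, it sends every predose, 1-hour and 12-hour dosing-day sample to the local laboratory and leaves the central vendor none. A sample drawn at the wrong time cannot be retaken.

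**Working it through.** **1. The plan's own figure.** Section 9.9 gives about 84% for passing the Part 2 rule with CV 30% and 15 active participants. The log-scale SD is √ln(1 + 0.30²) = 0.2936. With a non-informative prior, and using the active arm at one time point, the rule is met when (mean − ln 1.5)/(s/√15) ≥ t(0.60, 14) = 0.258. At a true fold of exactly 1.5 this gives 40%. It gives 84.2% at a true fold of about 1.65. Section 9.9 assumes only a fold of at least 1.5, so 84% cannot be reproduced from its stated inputs. Nothing below depends on it.

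**2. Which laboratory gets which sample.**
- Central row of the Schedule: 2 (Day 1) + 6 single draws + 2 (Day 22) + 10 later = 20. Appendix 8 budgets 19 + 1 = 20.
- Local row: 1 (screening) + 3 (Day 1) + 5 × 2 (Days 3, 5, 8, 15, 22) + 11 single draws = 25. Appendix 8 budgets 1 + 23 + 1 = 25.
- The 8.9.1 local list taken literally: 1 + 6 × 3 + 9 other days (10, 17, 23, 24, 26, 29, 35, 42, 111) = 28, not 25. It would leave the central vendor only Days 2, 49, 63 and 81, four visits against 20 budgeted draws, and would remove Day 29, the hypothesis time point.

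The Schedule and Appendix 8 therefore agree, and 8.9.1 is a loose sentence. The 25 local samples leave no room for local predose samples after Day 1.

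Seven visit days lie between Days 1 and 22 (2, 3, 5, 8, 10, 15, 17) against six single central draws. Column alignment is lost in the text available, so one of those days may have no central draw, and it cannot be said which.

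**3. Which weekly points are open.** Maintenance doses fall on Days 8, 15 and 22, so 168 hours after each is Day 15, 22 and 29. Day 22 has a timed predose draw and Day 29 is not a dosing day. Only Day 15 is open. The other candidate set, Days 8, 15 and 22, leaves two open but omits the only time the hypothesis concerns.

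**4. Predose or 1 hour.** The central note mentions a 1-hour draw only on days with two draws. The hypothesis is at 168 hours, and 4.3.4 states the target at trough. Footnote b already puts a predose draw before dialysis.

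**5. Size at the projected exposure.**
- Section 4.3.4 projects over 90% of participants at 1.5-fold at trough. At CV 30% the geometric mean is at least exp(ln 1.5 + 1.2816 × 0.2936) = 2.185.
- Projected Cmax is 91 nM. Scaling the 40 mg single-dose Cmax (78.2 nM) to 25 mg gives 78.2 × 25/40 = 48.9 nM, so trough is about 91 − 48.9 = 42.1 nM.
- Section 4.3.3 gives about 2.75-fold at 80 nM and 2-fold at 20 nM. A line in ln(concentration) has slope 0.75/ln 4 = 0.541. It gives 2.82 at 91 nM and 2.40 at 42.1 nM, a ratio of 1.173.
- A 1-hour draw would then report 2.185 × 1.173 = 2.56 instead of 2.19, about 17% higher.
- The single-dose 40 mg ratio, 2.75/2 = 1.375, would give 3.00 (38% higher). It belongs to a fourfold fall in concentration (80 to 20 nM), whereas Part 2 projects 91/42.1 = 2.2-fold, and 3.00 exceeds the 2.82 peak on the line.

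**6. Effect on the rule.** At 2.185 the log mean lies (ln 2.185 − ln 1.5)/(0.2936/√15) = 0.376/0.0758 = 4.96 standard errors above the threshold, against a cut-off of 0.258. A single trough point passes with probability above 0.9999, so Day 22 or Day 29 settles the matter whatever Day 15 shows.

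**7. Hypothetical low troughs.** In simulations with assumed within-participant correlations of 0.3 to 0.9, a true trough of 1.3 passes 3–5% of the time with three trough draws and 49–98% with one peak draw. At 1.4 the figures are 18–29% and 83–99.9%. These assume every participant was drawn at 1 hour that day. On the line above, 1.3-fold corresponds to about 20 × exp(−0.7/0.541) = 5.5 nM, against the derived trough of 42.1 nM.

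**The case for a change.** The strongest contrary case is that neighbouring rows are timed and this one is not, so a site could draw at 1 hour in good faith. The rule tests fold change from baseline rather than the ratio to placebo, so placebo would not remove a heparin effect. The dose is stated as up to 25 mg and may be lowered, and 8 mg gave at most 1.4-fold in healthy participants (4.3.2), so a trough below 1.5 is conceivable. The weekly fold changes also inform dose selection in later trials.

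The textual gap stands: the label is missing, the three days are unnamed, and 8.9.1 does not fit the Schedule. It does not follow that the analysis would go wrong. Section 6.6.1 shows that the authors know 1-hour values are distorted, and nothing in the plan suggests using one as a weekly value. Sections 8.8 and 8.9.1 leave collection instructions to manuals that are not among the documents, so it cannot be said that sites lacked the time. Table 7 holds Part 2 samples in the first four hours after a dose to 5 minutes, so a 1-hour sample should be identifiable from its recorded time, assuming times are recorded as is usual.

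That any one of three points can satisfy a hypothesis about a single time is a separate question. Labelling the draws and naming the days would leave it as it is.

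**Conclusion.** No change to the plan follows. This is missing detail that the analyst can fill from the hypothesis, the trough rationale and the sample counts: predose draws, most naturally on Days 15, 22 and 29. The 8.9.1 wording is a clerical slip that the Schedule and Appendix 8 resolve. On that reading one draw, Day 15, is open. If it were taken at 1 hour, that day's fold change would read about 17% high, while the rule and the Day 29 results would be unaffected.

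This rests on the 25 mg projection in 4.3.4, CV 30%, aPTT fold change linear in log concentration, and no heparin effect. Heparin would raise a 1-hour value further by an amount the documents do not give. The large swings in pass probability arise only at assumed troughs below 1.5-fold, which the protocol does not project for 25 mg.

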
- Objective:
 
Part 1: To evaluate the effect of MK-2060 on aPTT following single dose IV administration in older adult participants with ESRD on HD.
 
Part 2: To evaluate the effect of MK-2060 on aPTT following multiple dose IV administration including an IV loading dose in older adult participants with ESRD on HD.
 
- Hypothesis:
 
Part 1: The true fold increase from baseline for aPTT 168 hours after a single well-tolerated dose of MK-2060 in older adult participants with ESRD on HD is at least 1.5.
 
Part 2: The true fold increase from baseline for aPTT 168 hours post the last dose following an IV loading dose and three maintenance IV doses of MK-2060 in older adult participants with ESRD on HD is at least 1.5.
	
- aPTT fold change from baseline

Part 1:
 
- Objective: To compare the plasma pharmacokinetics of MK-2060 following a single dose IV administration in older adult participants with ESRD on HD to participants with normal renal function (historical controls in PN001).
 
- Estimation: In older adult participants with ESRD on HD, PK parameters (e.g. AUC_{0-∞}, C_{max}) of MK-2060 following administration of a single dose will be estimated and compared to participants with normal renal function (historical controls in PN001).
	
- Part 1: MK-2060 plasma AUC_{0-∞}, AUC₀₋₁₆₈, C_{max}, C₁₆₈, T_{max}, terminal t_{1/2}, CL and V_d

Overall Design:

Study Phase	Phase 1		
Primary Purpose	Treatment		
Indication	Prevention of thrombotic complications		
Population	Patient: Older adult participants with end-stage renal disease on hemodialysis		
Study Type	Interventional		
Intervention Model	Sequential This is a multi-site study.		
Type of Control	Placebo		
Study Blinding	Double-blind		
Masking	Participant or Subject	Investigator	Outcomes Assessor
Estimated Duration of Study	The Sponsor estimates that the study will require approximately 23 months from the time the first participant (or their legally acceptable representative) provides documented informed consent until the last participant's last study-related contact.		

Number of Participants:

Approximately 44 participants will be allocated/randomized.

Intervention Groups and Duration:

Intervention Groups	Intervention Group Name	Drug	Dose Strength	Dose Frequency	Route of Administration	Regimen/Treatment Period	Use				
	Part 1										
Panel A	MK-2060	8 mg	Once	IV	Single 60-minute IV infusion	Experimental					
	Placebo ^a	Placebo ^a									

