4.2.1.3 Pharmacodynamic Endpoints

aPTT and FXI activity (performed by Central Lab); fibrin generation assay (FGA) and high sensitivity C-reactive protein (hsCRP)

In order to assess PD, this study will include an assessment of aPTT prolongation levels (relative to baseline), and FXI activity levels, with assays being performed at a Central Laboratory. For PK/PD modeling, aPTT and FXI activity levels will be related to plasma exposure. FGA and hsCRP will also be measured as exploratory PD biomarkers. The time points for PD data collection are based on the projected PK profile of MK-2060. Estimation of the aPTT effects of MK-2060 following a single and multiple well-tolerated

dose is a secondary objective of this study. For this secondary objective, the hypothesis that is being tested is: The true fold-increase in aPTT 168 hours after a single well-tolerated dose of MK-2060 in older adult participants with ESRD on HD is at least 1.5 (Part 1) and the true fold increase from baseline for aPTT 168 hours post the last dose following an IV loading dose and three maintenance IV doses of MK-2060 in older adult participants with ESRD on HD is at least 1.5 (Part 2). A 1.5-fold aPTT prolongation corresponds to the in vitro PD effect that is observed when using a concentration of MK-2060 that was demonstrated to inhibit clot formation in nonhuman primates to a similar extent as a clinically relevant comparator (apixaban, 5 mg bid). In plasma from severe FXI-deficient patients, aPTT prolongation up to 3.9-fold is observed, using the same PD assay described above [Ellsworth K 2018]. aPTT prolongation up to approximately 3.5-fold was also reported in FXI-deficient subjects in a published study [Asakai, R., et al 1991]. aPTT prolongation up to ~4-fold would be expected for almost complete FXI inhibition, and aPTT prolongation greater than 4-fold would represent unexpected pharmacology, which is part of the basis for the aPTT-based stopping rules described in Section 6.6.1

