4.3.4 Rationale for Multiple Dose Regimen (Part 2)

The primary intent of Part 2 is to evaluate the safety, tolerability, PK, and PD of an MK-2060 multiple dose regimen that will achieve target anticoagulation. For anticoagulants, it is desirable to achieve near target anticoagulation as soon as therapy is initiated so a loading dose is being used for this portion of the study. 40 mg IV is the highest dose assessed in PN001 in NHVs and in ESRD patients in Part 1 of PN004. In PN001 with a single 40 mg IV dose Cmax and AUC_{0-168hr} the geometric mean (GCV) were 78.2 (11.8) nM and 6350 (17.6) nM*hr, respectively. Preliminary dose modelling based on PK/PD data from the available 8, 20, and 40 mg single dose data in ESRD patients in Part 1 of PN004 projects that a regimen of 25 mg dosed on Days 1, 3, and 5 followed by 3 maintenance doses of 25 mg QW is projected to have a median Cmax (post first maintenance dose) of 91 nM and AUC_{0-168hr} (post last dose) of 8868 nM*hr. From a safety perspective, the steady state Cmax of the 25 mg IV QW dose is projected to be \sim 25% higher than the Cmax achieved with the 40 mg IV single dose in PN001. Due to the slight increase in projected steady state Cmax in Part 2, the domiciling period has been increased during the first week of dosing for additional safety monitoring. As discussed above, all doses of MK-2060 have been generally well tolerated with no dose related SAEs, discontinuations due to AEs, or AEs suggestive of hypersensitivity, therefore no safety issues are anticipated in Part 2 with this slightly higher exposure. 25 mg QW is projected to result in $>90\%$ of participants with aPTT of 1.5 fold baseline at trough. The multiple dose regimen of Part 2 (3 doses for week 1 plus 3 maintenance doses) steady state is projected to be achieved by end of week 1 (concentration \sim 90% of steady state).

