In Part 2 (multiple dose), in order to mimic the therapeutic setting, 3 doses given on Days 1, 3, and 5 will be studied in addition to the weekly maintenance dose. A weekly maintenance dosing frequency was selected to reduce the peak to trough ratio without posing a significant burden to ESRD patients who undergo dialysis 3 times a week and can receive an IV infusion concurrent with dialysis. A less frequent dosing interval would result in higher peak concentrations and patients being sustained at maximal FXI inhibition levels longer, which could potentially increase bleeding risk in this vulnerable population. For anticoagulants, it is desirable to achieve near target anticoagulation as soon as therapy is initiated. Given the half-life of ~18 days observed in Part 1 of PN004 and the dosing frequency of QW, without the 3 doses given during week 1 (loading dose) it would take weeks to achieve steady state exposure and target anticoagulation. Thus, the 3 doses during week 1 are introduced to help achieve desired anticoagulation immediately after initiation of therapy.

Participants will be discharged following the ~52- or ~24-hour (24 hours after last dose for Week 1 and 24 hours after each dose in Weeks 2-4) in-clinic period after dosing for Part 1 or Part 2 accordingly, but they will continue to be monitored throughout the trial period and return to the site post-dose as specified in the SoA (safety evaluations as indicated in the flow chart (including repeat physical examinations, infusion reaction assessments, laboratory safety assessments, hemoccult, local lab aPTT and PT tests).

Following discharge, the following measures are being taken in this protocol to ensure the safety of study participants:

- Participants will be informed that they could be taking an anticoagulant as a participant in this trial, and that this might increase the risk of bleeding as might occur in surgery, dental procedures, or strenuous exercise/contact sport activities.
- Participants will be excluded if they have planned significant dental procedures, including surgery, or other planned surgical procedures within duration of participation in the trial.

- Participants will be required to avoid scheduling any surgical or dental procedures, and to avoid strenuous physical activity and contact sport activities for the duration of the trial.

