9.3 Hypotheses/Estimation

Secondary

1. **Hypothesis (Part 1):** The true fold increase in aPTT 168 hours after a single well-tolerated dose of MK-2060 in older subjects with ESRD on HD is at least 1.5.
2. **Hypothesis (Part 2):** The true fold increase in aPTT 168 hours after the last dose following an IV loading dose and three maintenance doses of MK-20160 in older adult participants with ESRD on HD at least 1.5.

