Individual aPTT fold-change from baseline values will be natural log-transformed and evaluated with a linear mixed effects model containing fixed effects for treatment and time and treatment by time interaction and random effect for participant. Least squares means and 95% confidence intervals for each treatment, and for the between-treatment differences (MK-2060 – placebo) and 90% CI at each dose level, will be obtained by time. These estimates will be back-transformed to obtain GM aPTT fold-change from baseline by treatment and time and the GMR (MK-2060 fold-change from baseline/placebo fold-change from baseline) by dose and time.

The posterior probability that the true fold-increase from baseline in aPTT 168 hours after a single dose is at least 1.5 will be calculated for each dose assuming normality and using a non-informative (Jeffrey's) prior. A 60% posterior probability for at least one dose level that also exhibits an acceptable safety profile will satisfy the secondary pharmacodynamics hypothesis. In addition, the proportion of subjects with a fold-increase in aPTT 168 hours after a single dose of at least 1.5 will be tabulated.

FXI activity levels, FGA and PT will be evaluated in a similar fashion. Additional model-based analysis may be employed to further explore PD endpoints over time.

Descriptive statistics will be provided for PD endpoints by treatment and time.

Part 2:

As in Part 1, individual aPTT fold-change from baseline values will be natural log-transformed and evaluated with a linear mixed effects model incorporating the longitudinal effects of measurements at the three weekly time points. An unstructured covariance matrix will be used to model the correlation between different measurements within the same subjects. Kenward and Roger's method will be used to calculate the denominator degrees of freedom for the fixed effects. Least squares mean and 95% confidence intervals for each treatment, and for the between-treatment differences (MK-2060 – placebo) and 90% CI will be obtained. These estimates will be back-transformed to obtain GM aPTT fold-change from baseline by treatment and time and the GMR (MK-2060 fold-change from baseline/placebo fold-change from baseline) by time.

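### The Part 2 aPTT hypothesis concerns only 168 hours after the last dose (Day 29), but the success rule accepts any one of three unnamed weekly time points

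*Combined protocol and SAP*

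**What the plan says.** The hypothesis appears in four places, each time at a single time point.

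- Section 1.1, and again in Section 3: "The true fold increase from baseline for aPTT 168 hours post the last dose following an IV loading dose and three maintenance IV doses" is at least 1.5.
- Section 4.2.1.3: "the true fold increase from baseline for aPTT 168 hours post the last dose following an IV loading dose and three maintenance IV doses" is at least 1.5.
- Section 9.3: "The true fold increase in aPTT 168 hours after the last dose following an IV loading dose and three maintenance doses" is at least 1.5.

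Table 2 in Section 6.1 gives the Part 2 dosing days as 1, 3, 5, 8, 15 and 22, so 168 hours after the last dose is Day 29. The Part 2 schedule takes central-laboratory aPTT on Day 29, and Table 7 allows no day window for it.

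Section 9.6 (Pharmacodynamics, Part 2) fits a "linear mixed effects model incorporating the longitudinal effects of measurements at the three weekly time points". It calculates the posterior probability of at least a 1.5-fold increase at each of those times and then gives the decision rule: "A 60% posterior probability for at least one of the three time points that also exhibits an acceptable safety profile will satisfy" the secondary hypothesis. The following sentence returns to the hypothesised time: "the proportion of subjects with at least 1.5 fold increase in aPTT 168 hours after the last dose will be tabulated".

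**The concern.** The rule and the hypothesis refer to different quantities. The hypothesis is about Day 29; the rule is met by the best of three weeks. A trial in which Day 29 misses but another week passes would be reported as satisfying a hypothesis about Day 29. Geometric mean fold changes by time are also planned, so the miss would be visible, but the declared conclusion would contradict it.

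The three days are also undefined. Days 15, 22 and 29 (168 hours after each maintenance dose) is the natural reading. The schedule would also allow Days 8/15/22 or 29/35/42, and on the first of these Day 29 would not be tested at all. A smaller point is that the rule ties acceptable safety to a time point, whereas safety belongs to the regimen.

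**Working it through.** **Inputs from the documents.** 15 active and 5 placebo, true CV 30% (Section 9.9); threshold 1.5, posterior probability 60%, non-informative prior (Section 9.6).

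**Assumed, because the documents give none.** Within-participant correlation between weeks of 0.5 to 0.9; the true fold values; Days 15/22/29 as the three time points.

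**Criterion at one time point.** Log-scale SD = sqrt(ln(1 + 0.30²)) = 0.2936. For the active arm, SE = 0.2936/√15 = 0.0758. Posterior probability ≥ 60% is equivalent to (mean log fold − ln 1.5)/SE ≥ t(0.60, 14 df) = 0.258, with SE estimated from the data. At the assumed SD this is an observed geometric mean fold of about 1.5 × exp(0.258 × 0.0758) = 1.53. The chance of passing at Day 29 is a noncentral t tail with noncentrality ln(true fold/1.5)/0.0758.

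**The plan's own figure.** Section 9.9 gives about 84% for Part 2 and says only that the true fold is at least 1.5. At exactly 1.5, one time point passes with probability 40%. Any of three passes with probability at most 1 − 0.6³ = 78.4% (independent times). So 84% is not reproduced under either rule at 1.5. A single time point reaches it at a true fold of about 1.65 (active arm) or 1.81 (relative to placebo), and the plan states neither value. Section 9.9 therefore does not show which rule was intended.

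**Day 29 alone versus any of three.** Simulation with 200,000 trials per setting, exchangeable correlation, each time point analysed separately in the active arm; the placebo arm and the joint mixed model are left out. The Day 29 column agrees with the exact noncentral t. Ranges run from correlation 0.9 to 0.5.

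| True fold at the three times | Day 29 alone | Any of three |
|---|---|---|
| 1.40, 1.40, 1.40 | 12% | 18-26% |
| 1.45, 1.45, 1.45 | 24% | 33-45% |
| 1.36, 1.38, 1.40 | 12% | 14-20% |
| 1.41, 1.43, 1.45 | 24% | 28-38% |
| 1.60 at all three | 72% | 81-91% |
| 1.80 at all three | 98% | 99-100% |
| 2.00 at all three | 100% | 100% |

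The first four rows are false successes, because Day 29 is truly below 1.5. In the flat 1.45 row, 9-21% of trials succeed although Day 29 misses (0.328 − 0.242 to 0.451 − 0.242).

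**Why rising troughs are plausible.** Section 4.3.5 reasons from "Given the half-life of ~18 days observed in Part 1 of PN004 and the dosing frequency of QW". A one-compartment sketch with an 18-day half-life and the 25 mg doses considered in Section 4.3.4 gives pre-dose amounts of 62.0, 66.4, 69.8 and 72.4 mg on Days 8, 15, 22 and 29. These are drug amounts, so the fold steps in the table remain assumptions.

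**Where the effect is expected to lie.** Section 4.3.4 projects more than 90% "of participants with aPTT of 1.5 fold baseline at trough". If fold values are log-normal with CV 30%, 90% at or above 1.5 implies a median of 1.5 × exp(1.2816 × 0.2936) = 2.19. There the two rules agree.

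**The case against.** The strongest reply concerns importance. Section 9.8 notes that there are no primary hypotheses, and nothing ties escalation, stopping or sample size to this declaration. Section 4.2.1.3 describes the aim as estimation, and estimates by time will be shown. This stands, and it limits the weight of the point. It does not reconcile the texts: Section 9.8 is about multiplicity adjustment, not about which time decides the hypothesis.

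A second reply is that Part 1 also uses an at-least-one rule. That rule chooses among dose levels and keeps the time at 168 hours, as its hypothesis does. Part 2 has one regimen and varies the element its hypothesis fixes. The safety clause does look like a carry-over from the Part 1 wording, and no practical consequence of it has been shown.

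A third reply is that the numbers depend on the reading of the analysis. This stands in part. Section 9.6 says from baseline, which supports the active-arm calculation, but Section 9.9 speaks of an effect relative to placebo. With 15 versus 5 and pooled variance, SE = 0.2936 × √(1/15 + 1/5) = 0.1516 with 18 df. Day 29 alone versus any of three is then 24% versus 33-45% at a flat 1.40, 57% versus 67-81% at 1.60, and 83% versus 89-96% at 1.80. False success is higher under both rules, and the rules no longer nearly agree at 1.8.

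Finally, Days 15/22/29 is an inference. If Day 29 is not among the three, the simulated comparison does not describe the rule, and the mismatch with the hypothesis is greater.

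**Conclusion.** The concern holds, and it rests on the text alone: four sections fix the time at Day 29 and the decision rule does not. The simulation shows only how much this could matter. When the true Day 29 fold is 1.40 to 1.45, the any-of-three rule adds about 2 to 8 (at 1.40) or 4 to 14 (at 1.45) percentage points of false success with rising troughs, and about 6 to 14 or 9 to 21 points with a flat profile. These sizes assume CV 30%, correlation 0.5 to 0.9, Days 15/22/29 and an active-arm posterior. At the effect the sponsor projects, the choice of rule would not change the conclusion. It should be fixed, because a decision rule is written for the case where the projection fails, and Section 2.1 says the data will inform dose selection in later trials.

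**What to change.** In Section 9.6, Part 2, replace the any-of-three rule with wording such as: *The hypothesis is satisfied if there is at least 60% posterior probability that the true fold increase from baseline 168 hours after the last dose (Day 29) is 1.5 or more, with an acceptable safety profile for the regimen.* Name the study days of the three modelled weekly time points, including Day 29, and report the other two as supportive. If the sponsor does intend success at any week, keep the rule and restate the hypothesis in Sections 1.1, 3, 4.2.1.3 and 9.3. Either way, tie the probability of success in Section 9.9 to the rule chosen.

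No new data are needed, since Day 29 is already sampled. The cost is a lower chance of success when the effect is real but modest: at a true fold of 1.6, 72% instead of 81-91% (active arm), or 57% instead of 67-81% (relative to placebo). At 1.8 or more almost nothing is lost in the active-arm analysis; relative to placebo, the chance at 1.8 is 83% instead of 89-96%.
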